Identification: Each day, NICU admissions will be reviewed via the electronic medical record and infants who are born with a birthweight of less than 1500 grams will be identified. On day of life (DOL) 5-7, of those infants identified, those parents of infants who are still maintained on positive pressure ventilation and or >21% FiO₂, will be approached and consented for inclusion in the study.

Consent: Families will be approached in person in the Neonatal Intensive Care Unit or Post-Partum Unit between DOL 5-7 and consent obtained for participation in the study by [name] or [name]. One parental signature will be required. Written study material and copies of consent forms will be provided for families to keep. There will be no cost to the patient and no remuneration offered. Families may withdraw consent at any point of the study. See separate consent form, appendix 1.

Procedures: Consent will be obtained between DOL 5-7. Subjects will undergo block randomization. Once randomized, those patients who are assigned to standardized, scheduled prone positioning, will be placed in prone position, with the head turned either right or left per nursing or patient desire, for a total of 6 hours daily, during daytime hours, if clinically stable. They will be placed in prone position for 3 hours, followed by supine positioning for 3 hours, then placed in prone position for another 3-hour interval. If needed, position aids, which are part of the normal care routine in our ICU may be used to facilitate maintenance of prone or supine positioning. If an infant is felt to be too unstable, or significantly

intolerant of prone positioning, they may be positioned per nursing or patient comfort. If infant was already in the prone position per nursing routine prior to the start of prone positioning per study protocol, we will await change to a different position before initiating study protocol for infants assigned to scheduled prone positioning. This is to avoid infants being placed in prone position for > 3 consecutive hours at a time). Alternating between supine and position allows us to detect any short term immediate changes in oxygenation and vital signs attributable to a change in positioning between prone and supine.the two positions.

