Personnel: Neonatologists [name] and [name] will be responsible for consenting families and determining randomization assignment. Bedside nurses along with respiratory therapists will be responsible for position changes and documentation of physiologic metrics and vital signs as part of the normal ICU care practice. [name] will collect study data for analysis. Nurse practitioner [name], BSN, DNP, will be responsible for assigning the primary outcome of moderate or severe BPD, at or after 36 weeks post conceptional age. She will be provided a list of study participants identified only by study number at 36 weeks post conceptional age, their respiratory support parameters and will assign the primary outcome of moderate (Grade 2) or severe (Grade 3) BPD.

Randomization: Block randomization with variable block sizes will be performed in order to ensure equal sample sizes over time. The treatment (standardized prone positioning) ratio to control (usual positioning) ratio will be 1:1. The randomization list will be generated by the study statistician and will be maintained under locked conditions. Blinding of staff is inherently not feasible as scheduled prone position changes are obvious to caretakers.

Evaluations and measures: Incidence and severity of BPD will be assessed at 36 weeks post conceptional age. As part of usual NICU care, infants, especially those on respiratory support have vital signs and other physiologic parameters recorded routinely every 3 hours,

but this may occur as frequently as every hour in the sickest infants. Enrolled infants will have physiologic data and vital signs evaluated and recorded at start of hands-on time, at the 1 hour mark after scheduled position change to prone, at the time of switch to supine, 1 hour after 2nd switch to prone position, and at the time of conclusion of study positional changes. For infants randomized to usual care, we will record similar data from a period of 3 hands-on intervals (total of 9 hours).

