We aim to record and collect the following data once weekly on the weekly anniversary of the infantâ€™s first study prone positioning and the date of randomization onto the study for those study participants who were randomized to usual care: transcutaneous CO₂ (TCO₂) if available or PCO₂ from any blood gas, SaO₂ from cardiopulmonary monitors, PaO₂ from arterial blood gases within 1 hour of positional change (if available), ventilator or other respiratory support modality settings and direction of changes within 1 hour of positional change. Specifically, percent change in inspired oxygen, change in ventilator rate (breaths per minute), tidal volume (milliliters), peak inspiratory pressure (cm H₂O), positive end expiratory pressure (cm H₂O) and the number of episodes of oxygen desaturations will be collected. Current comorbidities, most recent chest x-ray findings within a 7day interval will also be documented once weekly.

Other data: duration of time on any respiratory support (days), duration of use of endotracheal tube, non-invasive positive pressure ventilation (NIPPV) and continuous positive airway pressure (CPAP), time to FiO₂ of 21% (irrespective of type of respiratory interface), type of medications to treat BPD (use of oral, inhaled or intravenous postnatal steroids for mitigation of BPD, caffeine, diuretics daily or intermittent), presence of pulmonary hypertension as documented by echocardiogram, use of sedatives and analgesics, pharmacologic treatment of

GERD, use of inhaled nitric oxide on DOL 7 or later. Additionally, the mode of ventilation at 7 days after birth, DOL when maximal feeds achieved (total fluids of 160 milliliters per kilogram per day), DOL at which feeding by mouth was initiated and DOL at which feeds were administered by mouth only, diagnosis of plagiocephaly, and the duration of NICU stay. Demographic data of interest include gestational age at birth (weeks), maternal comorbidities, infant comorbidities, growth status (small, appropriate or large for gestational age), weight at birth (kilograms) and use of antenatal steroids.

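### The listed session readings include none after time supine, body position is not recorded with readings, and the bedside card counts prone placements rather than hours, so the short-term prone-versus-supine effect and prone hours by arm can be estimated only approximately

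*Combined protocol and SAP*

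**What the plan says.** **Purpose.** The Procedures section gives a reason for alternating positions in the scheduled-prone arm: it "allows us to detect any short term immediate changes in oxygenation and vital signs attributable to a change in positioning between prone and supine". The session is 3 hours prone, 3 hours supine and 3 hours prone.

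**Readings.** Evaluations and measures lists five: at the start of hands-on time, 1 hour after the turn to prone, then "at the time of switch to supine, 1 hour after 2nd switch to prone position", and at the end of the study position changes. For usual care, "we will record similar data from a period of 3 hands-on intervals (total of 9 hours". The same section notes that infants have "vital signs and other physiologic parameters recorded routinely every 3 hours", and hourly in the sickest.

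**Weekly data.** The weekly list includes "ventilator or other respiratory support modality settings and direction of changes within 1 hour of positional change", and continues: "Specifically, percent change in inspired oxygen, change in ventilator rate". SaO₂ is on this list; vital signs are not. It does not say which turn the 1-hour window refers to.

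**Position.** An infant already prone before a session must first be moved: "we will await change to a different position before initiating study protocol". The Background says usual positions include lateral. Infants who are too unstable, or who are "intolerant of prone positioning, they may be positioned per nursing or patient comfort", leave the schedule. No body-position item appears in either list of readings.

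**Exposure.** Under Procedures, the bedside card in both arms records how many times an infant is placed prone. It does not record for how long. The Study plan describes 3-hourly repositioning for most infants when stable, and calls the time spent in each usual-care position random.

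**The concern.** The alternating session is a small within-infant crossover, well suited to the short-term question. Answering that question takes values under both positions, ideally just before and some time after each turn. The listed readings sample the prone blocks four times and the supine block not at all. The one reading not taken after study prone time, at 0 h, may have been taken with the infant lateral.

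Position can mostly be inferred from the schedule in the prone arm. It cannot be inferred in usual care, at 0 h, or when an infant is positioned for comfort.

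The intervention is defined in hours (6 per day), and usual-care infants may also lie prone. The pilot's stated goal is preliminary effect sizes, and an effect size is hard to carry into a later trial if the achieved difference in prone hours between arms is known only through a count.

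**Working it through.** The plan gives no figure on this point, so there is none to reproduce. Its one precision statement concerns the BPD rate difference and does not bear on this.

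**1. Readings placed on the session** (session from Procedures; readings from Evaluations and measures)

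| Time | Infant has been | Listed as a study reading |
|---|---|---|
| 0 h | not prone; supine or lateral | yes |
| 1 h | prone 1 h | yes |
| 3 h | prone 3 h (if read before the turn) | yes |
| 4 h | supine 1 h | no |
| 6 h | supine 3 h | no; probably charted routinely |
| 7 h | prone 1 h | yes |
| 9 h | prone 3 h | yes |

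There are two turns between study prone and study supine, at 3 h and 6 h. A before reading and a 1-hour-after reading need the pairs (3, 4) and (6, 7). The five listed readings complete 0 of 2. With the charted 6 h value they complete 1 of 2, and with 4 h and 6 h listed, 2 of 2.

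**2. Precision of the within-infant contrast, per session**

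Model: y(t) = m + d·prone(t) + b·t + e(t), where d is the prone-minus-supine effect, b a steady drift per hour, and e has variance s². Assumptions: the position effect is present by 1 h, the 3 h reading precedes the turn, and residuals are independent.

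- *y(1) − y(0), listed readings only.* Variance 1 + 1 = 2 s². It carries one hour of drift and starts from a position that may be lateral.
- *Listed readings plus charted 6 h.* The best drift-free weights on 1, 3, 7 and 9 h are 0.15, 0.20, 0.30 and 0.35, against y(6). The weights sum to 1. Weighted time is 0.15×1 + 0.20×3 + 0.30×7 + 0.35×9 = 6.00 h, so drift cancels. Variance: 1 + (0.0225 + 0.0400 + 0.0900 + 0.1225) = 1.275 s².
- *With 4 h and 6 h as study readings.* Mean of (1, 3, 7, 9) minus mean of (4, 6). Both mean times are 5 h, so drift cancels. Variance: 4×0.25² + 2×0.5² = 0.25 + 0.50 = 0.75 s².

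Ratio: 0.75/1.275 = 0.59. The standard error ratio is √0.588 = 0.77.

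**3. Sensitivity to autocorrelation**

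The correlation between readings at t and u is taken as ρ^|t−u|. The variance is the position entry of (X′R⁻¹X)⁻¹, with columns for intercept, position and time, so both sides are optimally weighted. The values of ρ are assumptions; the documents give none.

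| ρ per hour | Listed + 6 h | Listed + 4 h and 6 h | Ratio |
|---|---|---|---|
| 0 | 1.275 | 0.750 | 0.59 |
| 0.3 | 1.040 | 0.617 | 0.59 |
| 0.5 | 0.797 | 0.496 | 0.62 |
| 0.8 | 0.322 | 0.212 | 0.66 |

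**4. Prone hours from a count**

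Suppose the two scheduled prone periods are kept at 3 h each. Let a be the prone arm's other prone placements per day, with mean length m_P, and k the usual-care prone placements, with mean length m_U.

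- True separation: 6 + a·m_P − k·m_U
- Separation from count × 3 h: 6 + 3a − 3k
- Error: a(3 − m_P) − k(3 − m_U)

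The error is zero if every placement lasts 3 h. Otherwise its sign depends on a, k, m_P and m_U, none of which the documents give. Placements cut short and placements running over two touch intervals push it in opposite directions.

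**The case against.** The strongest reply is that most of what is needed already exists.

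- **The 6 h value.** The end of the supine block is a touch time, routine charting is 3-hourly, and study data come from the electronic record. The start of hands-on time could even be read as every touch time, including 6 h.
- **The weekly list.** Its 1-hour window is not restricted to turns to prone, so its ordinary reading may cover respiratory settings after the switch to supine. Its change measures need a value from before the turn. The 0 of 2 count is thus true only of the five-reading list.
- **The card.** Count times 3 h is a fair conversion wherever 3-hourly repositioning holds.
- **The stakes.** Statistical Considerations specifies no within-infant prone-versus-supine analysis and treats all results as exploratory. The gain also depends on weighting: if the six-reading contrast uses plain averages while its comparator is optimally weighted, the ratio at ρ = 0.3, 0.5 and 0.8 is 0.62, 0.70 and 0.91.

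Much of this stands, and it is why the conclusion says approximately. It does not close the gap. The 6 h value is not a listed study reading, and a 4 h vital-sign value exists only for infants charted hourly, who are the sickest. The weekly window names no turn, and its list omits vital signs, which the stated purpose includes. Nothing in the reply supplies position in usual care or after a departure from the schedule. The 3-hour rule is described for most infants when stable, and the plan's guard against longer continuous prone time is stated only for the scheduled-prone arm.

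**Conclusion.** The point holds as a gap in what is measured. As written, the plan answers its own short-term question less well than its design allows, and it describes achieved exposure only through a count. Against the listed readings plus a charted 6 h value, study readings at 4 h and 6 h reduce the contrast variance to 0.59 of its value under independence, and to 0.59–0.66 at the autocorrelations tried. This assumes linear drift, a position effect present by 1 h, and optimal weighting on both sides. The textual gap does not depend on these figures.

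Three stronger readings are tempting and are not supported:

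- *That the prone-versus-supine question cannot be answered.* Routine charting and the weekly change measures allow an approximate answer.
- *That the card overstates, or understates, the separation between arms.* The direction of error cannot be determined from the documents.
- *That the BPD result is compromised.* The outcome at 36 weeks and its intent-to-treat comparison use neither the session readings nor the card.

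The change is worth making, but the trial's main comparison does not hinge on it.

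**What to change.** - Align Procedures, Evaluations and measures, and the weekly data list in one reading schedule. Add study readings 1 hour after the switch to supine and at the end of the supine interval. State that readings at a turn are taken just before it. List the variables for each reading, including SaO₂ and vital signs.
- Record actual body position with every study reading, in both arms.
- Have the existing bedside card record prone start and stop times, or position at each 3-hourly touch time, in both arms. Report mean prone hours per day by arm.
- Keep the between-arm mixed models unadjusted for position, as the intent-to-treat comparison. Use recorded position only in a separate exploratory within-infant prone-versus-supine analysis, mainly in the prone arm, where position is scheduled.

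The cost is one or two extra readings per weekly session (the end-of-supine reading coincides with routine charting), one field per reading, and slightly more charting on the card. Positioning, randomization and the planned between-arm models do not change.

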Both infants randomized to standardized prone positioning and usual positioning will have a bedside card card identifying that the infant is a study participant and will serve as a way to document the number of times any infant enrolled in the study is placed in prone positioning even if not randomized to standardized prone positioning. The bedside card also facilitates the infantâ€™s nurse being aware of the time of day for prone into supine position change for those who are randomized to prone positioning. On the weekly anniversary of the infantâ€™s first placement in prone position for the study, physiologic and clinical data will be retrieved.

Risk/Benefit: anticipated medical, social, psychological, and/or legal risks are minimal; however uncommon risks to be being placed prone may include movement or dislodgement of a breathing tube or of an intravenous (IV) catheter. These uncommon risks will be minimized by staff paying strict attention to the positions of these devices during movement from prone to supine position and vice versa. Additionally, documentation of the positions of these devices is routine and will permit tracking of change in position of the devices. Potential benefits include a decrease in the severity and occurrence of moderate to severe BPD, a common condition of the lung related to premature birth.

Data storage and maintenance of confidentiality: Data will be reviewed and retrieved from the electronic medical record into a computerized study data form kept on a password protected computer in a locked office. Only the 2 study personnel, [name] and [name] will access study files to check or edit data. Consent forms will also be kept in a locked office. The study database will be permanently deleted and paper data collection tools will be shredded. Subjects will not be video or audiotaped during this study.

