that patient characteristics are distributed similarly across groups. The difference between the intervention and control arms in the rate of BPD at 36 weeks post-conceptional age and other outcomes will be estimated, along with corresponding 95% confidence intervals. In exploratory analyses, the chi-square test will also be applied to assess whether the rates of BPD and other binary outcomes are significantly different between groups, and the two-sample t-test will be used compare the mean values of continuous variables measured at a specific visit. Logistic and linear regression models will also be fit to the data to adjust for any baseline characteristics that are not balanced across groups despite randomization. Weekly physiologic, ventilator and other clinical data will be obtained and analyzed using generalized linear mixed models, with the logit link for binary outcomes and the identity link for continuous outcomes, to account for the correlation in repeated measures from the same infant. Missing data will be handled by analyzing the available data as well as by multiple imputation using chained equations. All analyses will be based on the intent-to-treat approach, and results will be viewed as exploratory and hypothesis generating.

We plan to randomize a total of 60 patients 1:1 to intervention and control (N=30 per arm). Since this is a pilot trial, the goal is to obtain preliminary data on effect sizes. Therefore, formal power calculations were not performed. With 30 patients per arm, the precision, as measured by the width of the 95%CI, with which the true intervention effect (i.e., difference between groups) can be estimated is +/- 25% or better. For example, to gauge the magnitude of the primary outcome of BPD incidence and the potential benefit of standardized prone positioning, we evaluated 2019 BPD rates in our NICU. There were 107 patients described as VLBW at birth. Of those, 34 infants developed moderate to severe BPD, a rate of 31%. If the observed BPD rate is reduced to 21% in the intervention arm for a between group difference of

10%, then the corresponding width of the 95% CI for the true difference will be +/- 22%. We anticipate performing this pilot study over 2-3 years to account for yearly variations in the admission of VLBW patients.

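### No pre-treatment record of the weekly respiratory measures is explicitly scheduled, and the weekly mixed models name no baseline covariate

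*Combined protocol and SAP*

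**What the plan says.** **When data are collected.** Procedures ties retrieval to the weekly anniversary of the infant's "first placement in prone position for the study, physiologic and clinical data will be retrieved". Evaluations and measures repeats that anchor for the prone arm: "We aim to record and collect the following data once weekly on the weekly anniversary of the" infant's first study prone session. For usual care it uses "the date of randomization onto the study for those study participants who were randomized to usual care".

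**Readings within a day.** Evaluations and measures also states: "Enrolled infants will have physiologic data and vital signs evaluated and recorded at start of hands-on time", and then at set points around the turns. For usual care, similar data come from a nine-hour window. The text does not say on which days these readings are taken.

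**What describes the infant at the start.** "Demographic data of interest include gestational age at birth (weeks), maternal comorbidities, infant comorbidities, growth status", followed by birth weight and antenatal steroids. Among the other data is the ventilation mode seven days after birth. It is the only listed respiratory item dated near the start of prone positioning on day of life 7. Statistical Considerations mentions clinical variables measured at baseline but does not list them.

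**How the data are analyzed.** "Weekly physiologic, ventilator and other clinical data will be obtained and analyzed using generalized linear mixed models". That sentence gives link functions and the reason for a mixed model, but no baseline term. Baseline adjustment appears only for the logistic and linear regressions, and only for characteristics found to be unbalanced.

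**The concern.** A weekly anniversary first occurs one week after its anchor. By then prone-arm infants have had about a week of the intervention, so a first record taken at that point is an outcome and not a baseline.

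Starting severity varies widely here. The Study plan admits infants from a nasal cannula at 2 LPM, with no FiO2 minimum on the positive-pressure route, up to intubation or tracheostomy. Randomization is in blocks, and no stratification by severity is described. With 30 infants per arm, a chance difference in starting support would carry into the weekly comparisons, and stable differences between infants would stay in the error term. The imbalance-triggered adjustment cannot detect a difference in starting FiO2 unless starting FiO2 has been extracted.

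Statistical Considerations gives preliminary effect sizes as the pilot's goal, so the width of the intervals matters.

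**Working it through.** **The plan's own figure.** Statistical Considerations gives +/- 22% for BPD rates of 31% and 21% with 30 per arm. The unpooled Wald half-width is 1.96 × sqrt(0.31 × 0.69/30 + 0.21 × 0.79/30) = 0.2205, or +/- 22%. It reproduces, and it involves no weekly measure, so this point does not change it.

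**Chance imbalance.** The standard deviation (SD) of the difference in baseline means, in units of the between-infant SD, is sqrt(2/30) = 0.258. With a normal approximation:
- P(|difference| > 0.25 SD) = 2 × [1 − Φ(0.25/0.258)] = 0.33
- P(|difference| > 0.5 SD) = 2 × [1 − Φ(0.5/0.258)] = 0.053

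**Gain at a single visit.** Take a continuous outcome recorded as a level (for example FiO2), with correlation r between its day-0 and later value. The documents give no r, so 0.3 to 0.7 is an assumption. Adjustment multiplies the variance by 1 − r². The half-width is 1.96 × sqrt((2/30)(1 − r²)) and the equivalent sample size is 30/(1 − r²).

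| r | Variance factor | Half-width (SD) | CI narrower by | Equivalent n per arm |
|---|---|---|---|---|
| no covariate | 1 | 0.506 | – | 30 |
| 0.3 | 0.91 | 0.483 | 5% | 33 |
| 0.5 | 0.75 | 0.438 | 13% | 40 |
| 0.7 | 0.51 | 0.361 | 29% | 59 |

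**Gain for a mean over several weeks.** The planned analysis uses repeated measures, so the single-visit table is only a guide. Assume m = 6 weekly visits and one common correlation r among all values, including day 0. The variance factor is (1 + (m − 1)r)/m without the covariate, and that minus r² with it. The half-widths become:
- r = 0.3: 0.327 SD to 0.289 SD (variance 22% lower)
- r = 0.5: 0.387 SD to 0.292 SD (variance 43% lower)
- r = 0.7: 0.438 SD to 0.258 SD (variance 65% lower)

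**Where these gains do not apply directly.** Several listed measures are changes around a turn, such as percent change in inspired oxygen. A change already removes much of the infant's level, so these values of r have no basis there. The formula also does not carry over to the outcomes modelled with a logit link.

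**The case against.** A reader might infer that no pre-treatment physiologic data are collected at all and that the mixed models cannot be adjusted. The documents do not support that.

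- The readings at the start of a care session name no day. If they cover the first study day, the first one precedes the first study prone turn and is a pre-treatment value.
- Infants on support "have vital signs and other physiologic parameters recorded routinely every 3 hours", and under Data storage and maintenance of confidentiality, "Data will be reviewed and retrieved from the electronic medical record into a computerized study data form". Starting values should therefore be retrievable.
- Ventilation mode at seven days is collected and could serve as a partial baseline term, and the baseline clinical variables are unlisted, so the named items need not be exhaustive.
- Randomization prevents systematic bias. The weekly measures are secondary, and the plan calls its results exploratory.

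All of this stands, and it limits the point to specification and precision. It does not remove it. The two places that set collection days both use the weekly anniversary. Ventilation mode is a device category, and the text does not say whether it is noted before randomization or before the first session. A value that sits in the chart enters the analysis only if someone is told to extract it and the model is told to use it. At r = 0.3 the single-visit gain is small.

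**Conclusion.** The point holds as a gap in specification. The plan does not explicitly schedule a pre-treatment record of FiO2, SaO2, CO2 or support settings, and it states no baseline covariate for the weekly mixed models. Followed as written, it gives weekly comparisons that are less precise than they could be and more exposed to chance imbalance.

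The size depends on a correlation that the documents do not give. Over the assumed range, the single-visit CI for a continuous level outcome narrows by between about one-twentieth and just under three-tenths. The gain for a multi-week mean can be larger, under the further assumptions of six visits and a common correlation. No figure is claimed for change or binary outcomes. The estimate of the BPD difference is not put in doubt. The change is worth making because it costs little and serves the pilot's stated goal.

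**What to change.** 1. For both arms, extract from the chart the last support mode, FiO2, SaO2, CO2 (if available) and support settings before randomization, with date and time. Call this day 0.
2. For each weekly outcome recorded as a level, prespecify its day-0 value as a covariate in the mixed model, whether or not the arms look balanced.
3. For device-specific settings, which not every infant has at day 0, use day-0 support mode and FiO2 instead.
4. For within-session changes, prespecify either that session's pre-turn value or day-0 support mode and FiO2. On later dates the pre-turn value follows the start of treatment, so adjusting for it addresses the within-session effect only.
5. State whether the readings described under Evaluations and measures apply on the first study day, in both arms.

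The cost is one extra chart extraction per infant (60 in all) of values mostly charted already, and one term in most models. Support mode entered as a category uses a little more, so its grouping should be kept coarse and fixed in advance.
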